1. INTRODUCTION

Breast cancer is the most common invasive cancer in women with an estimated quarter of a million new cases every year in the US[1]. Estrogen positive breast cancers are the most common subtype and contribute to the majority of deaths from breast cancers. While endocrine therapies that target the estrogen-signaling pathway form the backbone of treatment and have shown significant improvement in survival, resistance to therapy is inevitable limiting overall response.

1.1. ESR1 mutations and endocrine resistance

Acquired mutations in *ESR1* (20-30%) have been described in metastatic breast cancer (MBC) patients exposed to estrogen deprivation with aromatase inhibitors (AI) [2-5]. *ESR1* mutations are uncommon in primary breast cancers and rarely observed after adjuvant AI suggesting clonal selection[6]. Though, recent studies have suggested that de novo *ESR1* mutations might be observed at low allele frequencies [7, 8]. Currently the use of AI or AI in combination with cyclin-dependent kinase (CDK) 4/6 inhibitors are recommended for first line treatment of ER positive MBC. Constitutive activation, through mutations in the ligand-binding domain (e.g. Y537S, D538G, S463P), leads to AI resistance and portend a shorter survival [6]. Though, these mutations may exhibit sensitivity to selective estrogen receptor down-regulators (SERD) (e.g. fulvestrant) that target mutant ER for proteasomal degradation[9]. In the BOLERO-2 study, which tested the use of exemestane alone or in combination with everolimus in MBC with prior exposure to AI, plasma *ESR1* mutations (D538G and Y537S only) were identified in nearly 30% of patients. While *ESR1* mutations were associated with shorter overall survival compared to wildtype (32 months), Y537S *ESR1* mutations (20 months) were associated with a worse outcome compared to D538G (26 months) suggesting differences in the variants [10]. In SoFEA trial, which compared the activity of fulvestrant versus exemestane against fulvestrant in combination with anastrozole in hormone-receptor (HR) positive metastatic postmenopausal women who had progressed on prior non-steroidal AI, plasma *ESR1* mutations were observed in nearly 40% of patients. In PALOMA-3 study, which evaluated the addition of CDK 4/6-inhibitor palbociclib to fulvestrant, approximately 25% of patients were found to harbor *ESR1* mutations in plasma, which did not appear to be predictive of palbociclib response. The lower prevalence of *ESR1* mutations in PALOMA3 likely reflects the inclusion of patients with primary resistance to endocrine therapy and prior tamoxifen exposure.

1.2. Circulating Tumor DNA

Improved understanding of tumor evolution and resistance has helped to underscore the importance of repeat biopsies. A major barrier to study genomic evolution and mechanisms of resistance is the challenge associated with obtaining serial tumor biopsies. Depending on the organ, biopsies are associated with procedural complications such as bleeding, pneumothorax, and infections. In a prospective study evaluating the use of biopsies in advanced breast cancers, only about 80% of patients undergoing biopsy had sufficient tissue for receptor analysis [11]. Moreover, more than 35% of biopsies from bone, commonest site of metastasis in hormone receptor positive breast cancers, had insufficient sample yield. Also, radiological assessment has limited sensitivity and cannot discern between cancer cells that are viable vs. non-viable or non-cancer cells such as fibroblasts.

Analyses of circulating tumor DNA (ctDNA) offer a minimally invasive, blood-based, approach to monitor disease and treatment response [12]. Unlike tissue biopsies, ctDNA avoids sampling bias due to intratumor heterogeneity and can provide an objective estimate of tumor burden. Quantitative changes in ctDNA were associated with a better dynamic range and correlation with tumor burden compared to tumor markers in MBC [13]. Assessing residual cancer burden with ctDNA has been shown to identify high-risk patients for relapse [14]. ctDNA analysis has been shown to identify *ESR1* mutations not discernable on tissue sampling [15]. Also, a high prevalence of polyclonal *ESR1* mutations has been reported, in patients previously treated with aromatase inhibitor endocrine therapy, suggesting that the complexities of resistant disease due to tumor evolution and heterogeneity is unlikely to be captured by single site tissue biopsy [9].

ctDNA dynamics has been shown to predict responses before such changes are evident on conventional approaches such as imaging. Thus, early ctDNA dynamics can act as a surrogate for assessment of

treatment efficacy with ability to transition from an ineffective therapy to a potentially active one. Furthermore, mutational allele frequency (MAF) represent tumor clones harboring a mutation, thus providing an indicator of tumor burden. Serial monitoring of MAF with ctDNA in patients treated with targeted therapies has been shown to be associated with time to radiologic disease progression [16]. Clatot et al. retrospectively analyzed *ESR1* mutations in ctDNA in patients who were treated with AI for MBC as first line [17]. *ESR1* mutations were identified in 31% of patients at progression with AI. Patients with *ESR1* mutations had worse median PFS (5.9 months) compared to patients without a mutation (7 months). In patients with *ESR1* mutations, 75% of them had detectable circulating mutations before clinical progression. Also, patients presenting with increases in circulating *ESR1* at 3 months after subsequent treatment with prior AI had disease progression. In the FERGI study, patients with radiologic response (complete or partial) demonstrated significant decreases in *ESR1* plasma MAF post treatment with fulvestrant and these were detected early in the course of response. ctDNA analysis of NSCLC patients treated with EGFR inhibitors, showed that EGFR T790M, a common mechanism of secondary resistance ctDNA was detected nearly 2 months prior to clinical progression and that the EGFR T790M ctDNA positive patients had significantly shorter survival [18]. ctDNA velocity with decrease in MAF at 6 weeks were shown to be predictive of response and associated with improved survival to durvalumab in lung cancer [19]. Similarly, in the study evaluating the efficacy of neratinib in advanced breast cancer patients with ERBB2 mutations, decrease in MAF at 4 weeks was predictive of clinical response [20].

ctDNA dynamics of PIK3CA mutations assessed in PALOMA-3 study [21]. Plasma samples were collected at baseline, Day 15, and at progression. A reduction in CDR15 (circulating DNA ratio, defined as the ratio of mutant copies/ml at Day 15 on treatment relative to baseline) to <1 in *PIK3CA* was associated with improvement in PFS seen with palbociclib and fulvestrant. Thus, serial measurements of ctDNA can help characterize genomic landscape, clonal evolution, response and predict for early recurrence. However, it is not clear whether treatment decisions can be made based on the appearance of resistance mutations or MAF changes in ctDNA and that “genomically adapted therapy” can improve outcome [22]. We hypothesize that real-time monitoring of ctDNA for secondary *ESR1* alterations can identify subclinical progression and early intervention with *ESR1* mutation-targeted agents can improve survival in ER positive MBC.

1.3. CDK inhibitors

Currently, CDK inhibitors e.g. palbociclib (Ibrance), ribociclib (Kisqali), and abemaciclib (verzenio) are approved for the first line treatment of HR positive advanced breast cancers in combination with aromatase inhibitors as well as in combination with fulvestrant with disease progression following prior endocrine therapy. Final approval of palbociclib is based on data from PALOMA-2, which randomized 666 postmenopausal women (2:1) to palbociclib plus letrozole or placebo plus letrozole [23]. The PFS was 24.8 months in the palbociclib plus letrozole arm and 14.5 months in the placebo plus letrozole arm (HR=0.576, 95% CI: 0.463, 0.718, p<0.0001). Palbociclib is also approved in combination with fulvestrant, based on PALOMA-3, which randomized (2:1) a total of 521 pre-and postmenopausal HR positive women with MBC, with disease progression on or after prior adjuvant or metastatic endocrine therapy, to either palbociclib plus fulvestrant or placebo plus fulvestrant until disease progression [24]. The median PFS was 9.5 versus 4.6 months for patients treated in the palbociclib plus fulvestrant and placebo plus fulvestrant arms, respectively. Approval of ribociclib was based on MONALEESA-2, a double blind, placebo-controlled, trial in post-menopausal women with HR-positive, advanced breast cancers who received no prior therapy [25]. A total of 668 patients were randomized to receive ribociclib plus letrozole (n=334) or placebo plus letrozole (n=334). The estimated median PFS had not been reached in the ribociclib-containing arm and was 14.7 months in the placebo-containing arm. Objective response rate (ORR) in patients with measurable disease was 52.7% (95% CI: 46.6, 58.9) in the ribociclib plus letrozole arm and 37.1% (95% CI: 31.1, 43.2) in the placebo plus letrozole arm. Abemaciclib was initially approved in combination with fulvestrant for HR positive MBC patients who had progressed on prior endocrine therapy. This was based on MONARCH-2, a double-blinded, placebo-controlled study that randomized 669 patients to receive fulvestrant with or without abemaciclib. Median PFS was 16.4 months in patients taking abemaciclib plus fulvestrant vs. 9.3 months with fulvestrant alone [26]. Abemaciclib is also approved in

combination with aromatase inhibitor as initial therapy for HR positive MBC patients, based on the findings from MONARCH 3, a randomized (2:1), double-blinded, placebo-controlled, study in HR positive postmenopausal women with MBC [27]. The estimated median PFS was 28.2 months in the abemaciclib-containing arm and was 14.8 months in the placebo-containing arm. In combination with endocrine therapy, CDK inhibitors are well tolerated with neutropenia, infections, leukopenia, fatigue, nausea, stomatitis, anemia, alopecia, diarrhea, thrombocytopenia, rash, vomiting, and decreased appetite being the most common adverse reactions.

1.4. Fulvestrant

Fulvestrant (Faslodex), a selective estrogen receptor antagonist, was initially indicated for treatment of HR positive MBC in post-menopausal women with disease progression following prior anti-

[figure not shown]

Figure 1: PFS in SoFEA study based on *ESR1* mutation. Panel-A PFS in patients with *ESR1* mutation treated with exemestane vs. fulvestrant containing regimen (A) Panel-B PFS in patients without *ESR1* mutation

estrogen therapy. It was recently approved by FDA as monotherapy for expanded use in post-menopausal women with HR positive advanced breast cancer, who have gone through menopause and have not received previous endocrine therapy. The FDA approval is based on data from the Phase III FALCON trial [28]. The FALCON trial is a Phase III, randomized, double-blind, multicenter trial that compared the efficacy and tolerability of 500mg dose of fulvestrant with anastrozole, in postmenopausal women with HR+, locally-advanced or metastatic breast cancer who have not received prior endocrine therapy. The study showed a statistically-significant increase in median PFS compared to anastrozole (16.6 vs. 13.8 months; HR: 0.797; $p=0.049$). The FALCON trial was designed on the basis of the Phase II FIRST trial, which demonstrated a median overall survival nearly six months longer with fulvestrant compared to anastrozole (54 vs 48 months; HR: 0.70; $p=0.049$)[29].

Currently, the most effective therapy for patients harboring *ESR1* mutations is unknown. While preclinical studies have shown reduced sensitivity to fulvestrant at clinically achievable concentrations, no differences in progression-free survival (PFS) were noted in patients with plasma *ESR1* mutations treated with fulvestrant compared to wild-type (WT) in FERGI study [30]. FERGI study compared the activity of pictilisib, a pan-PI3K inhibitor, with fulvestrant in HR positive MBC patients with prior exposure to AI [30]. *ESR1* mutations were observed in about 37% of patients and was enriched in luminal A subtype, with similar PFS in *ESR1* mutant and wild type patients, suggesting that mutations are not associated with clinical resistance to fulvestrant. In PALOMA-3 study, an improvement in median PFS for combination of fulvestrant with palbociclib in MBC patients who had progressed on prior endocrine therapy (9.2 months vs 3.8 months for fulvestrant alone; $P < 0.001$) was observed. However, the use of fulvestrant with palbociclib was associated with similar improvement in progression free survival (PFS) in both wild-type and mutant *ESR1* suggesting that mutational status does not affect response to palbociclib [5]. In SoFEA trial, those with *ESR1* mutations had prolonged PFS with fulvestrant compared with exemestane ($P = 0.02$) while no PFS difference was observed in WT *ESR1* [9]. Consequently, patients with *ESR1* mutations will be randomized to fulvestrant versus continuation of AI.

1.5. Guardant 360 Assay

ctDNA

Table-1 Guardant 360 ctDNA panel

Point Mutations (SNVs) (73 Genes)										Indels (23 Genes)		Amplifications (CNVs) (18 Genes)		Fusions (6 Genes)	
AKT1	ALK	APC	AR	ARAF	ARID1A	ATM	ATM	APC	AR	BRAF	ALK				
BRAF	BRCA1	BRCA2	CCND1	CCND2	CCNE1	CDH1	ARID1A	BRCA1	CCND1	CCND2	FGFR2				
CDK4	CDK6	CDKN2A	CTNNB1	DDR2	EGFR	ERBB2	BRCA2	CDH1	CCNE1	CDK4	FGFR3				
ESR1	EZH2	FBXW7	FGFR1	FGFR2	FGFR3	GATA3	CDKN2A	EGFR	CDK6	EGFR	NTRK1				
GNA11	GNAQ	GNAS	HNF1A	HRAS	IDH1	IDH2	ERBB2	GATA3	ERBB2	FGFR1	RET				
JAK2	JAK3	KIT	KRAS	MAP2K1	MAP2K2	MAPK1	KIT	MET	FGFR2	KIT	ROS1				
MAPK3	MET	MLH1	MPL	MTOR	MYC	NF1	MLH1	MTOR	KRAS	MET					
NFE2L2	NOTCH1	NPM1	NRAS	NTRK1	NTRK3	PDGFRA	NF1	PDGFRA	MYC	PDGFRA					
PIK3CA	PTEN	PTPN11	RAF1	RB1	RET	RHEB	PTEN	RB1	PIK3CA	RAF1					
RHOA	RIT1	ROS1	SMAD4	SMO	STK11	TERT**	SMAD4	STK11							
TP53	TSC1	VHL					TP53	TSC1							
** includes TERT promoter region										VHL					

analysis would be performed using the Guardant 360 assays (Guardant Health, Redwood City, CA). Guardant 360 is a CLIA-certified, CAP-accredited, New York State Department of Health approved digital sequencing technology for clinical cfDNA testing. The assay tests for SNVs (single nucleotide variations) in up to 73 genes, as well as indels, CNVs (copy number variations), and gene fusions in select genes. List of genes accessed by Guardant 360 is listed in **Table-1**. Patients with activating *ESR1* mutations identified on the Guardant 360 panel will be randomized into the study

1.6. Rationale

Nearly two-thirds of breast cancers overexpress estrogen receptor (ER) and estrogen blockade is an integral part of treatment. Currently the use of AI in combination with a CDK 4/6 inhibitor is recommended for first line treatment of ER positive MBC. Mutations in the ligand-binding domain of *ESR1* have been described in MBC patients exposed to estrogen deprivation with AI. These mutations have been demonstrated to mediate resistance to AI therapy limiting their clinical activity and portend a shorter survival. Presently, the most effective therapy for patients harboring *ESR1* mutations is unknown. Pre-clinical studies have suggested that fulvestrant, a SERD, is active in *ESR1* mutant breast cancers. Analyses of circulating tumor DNA (ctDNA) offer a minimally invasive approach to monitor disease and treatment response. Currently, treatment decisions are based on clinical disease progression and thus at the time of high disease burden. Real time monitoring with ctDNA can identify patients who exhibit subclinical recurrence or progression. Early detection and intervention with alternate therapy to overcome resistance at minimal disease burden progression could have a larger impact than treating higher burden disease at clinical progression. However, it is not clear whether treatment decisions can be made based on the appearance of resistance mutations in ctDNA and that "genomically adapted therapy" can improve outcome. The present study hypothesizes that real-time monitoring of ctDNA for secondary *ESR1* alterations can identify patients with subclinical progression and early intervention with *ESR1* mutation-targeted agents at minimal disease burden progression. This strategy also precludes patients from being exposed to treatments known to be associated with resistance and unlikely to offer clinical benefit.

2. TRIAL OBJECTIVES AND ENDPOINTS

2.1. Primary Objectives

- To assess progression free survival (PFS) with transition to fulvestrant compared with continuing AI therapy in patients with emergence of *ESR1* mutations in plasma

2.2. Primary Endpoints

- Progression free survival as assessed by Kaplan-Meier analysis

2.3. Secondary Objectives

- To assess ctDNA *ESR1* mutant allele fraction (MAF) and kinetics with fulvestrant compared with AI
- To assess the prevalence of *ESR1* mutations in patients with secondary resistance to endocrine therapy
- To correlate ctDNA with CA 15-3 tumor marker changes
- To assess overall survival (OS) with transition to fulvestrant compared with continuing AI therapy in patients with emergence of *ESR1* mutations
- To assess PFS and time to next treatment (TTNT) on next line of therapy after progression on fulvestrant vs. AI in combination with CDKI

2.4. Secondary Endpoints

- MAF
- CA15-3
- OS
- PFS
- TTNT

2.5. Exploratory Objective

- Characterize other co-existing actionable genomic alterations of interest in relation to *ESR1* and clinical outcomes
- To determine frequency of other actionable genomic alterations and frequency of enrollment on genotype-matched therapy

2.6. Exploratory Endpoints

- Concomitant genomic alterations will be explored in relation to clinical outcomes of interest, and in particular in relation to the primary endpoint of PFS

3. STUDY DESIGN AND SELECTION OF PATIENTS

While the estimates of *ESR1* mutations in advanced breast cancers have varied across studies, data from SoFEA and PALOMA3 show that *ESR1* mutations were typically associated with sensitivity to prior endocrine therapy and secondary resistance. Secondary or acquired resistance is defined as relapse while on adjuvant endocrine therapy after at least 2 years, or relapse within 12 months of completion of adjuvant endocrine therapy or relapse after 6 months of endocrine therapy for MBC [31]. SoFEA trial enrolled patients with no disease progression or relapse on non-steroidal AI for at least 12 months in the adjuvant setting or at least 6 months in the metastatic setting as first line treatment. In SoFEA trial, nearly 90% of *ESR1* mutations observed in MBC patients who had received AI for at least 12 months. While PALOMA3 study enrolled a more varied population, 93% of *ESR1* mutations were observed in patients who were deemed sensitive to prior endocrine therapy suggesting that *ESR1* mutations are seldom associated with primary resistance [9]. Consequently, to identify *ESR1* mutations, HR positive (ER >10%) MBC patients who are on AI with CDK4/6 inhibitor (palbociclib, ribociclib, or abemaciclib) as first line therapy for at least 12 months would be screened for ctDNA analysis. Patients with *ESR1* alterations in ctDNA would be enrolled and randomized.

It is anticipated that approximately 400 MBC patients who are on AI with CDK4/6 as first line therapy for at least 12 months will be screened for ctDNA analysis in order to identify approximately 124 eligible patients with *ESR1* alterations in ctDNA. For screening, approximately 20 mL of peripheral blood will be collected in Streck™ tubes (see **Table 1**). The results from the screening ctDNA tests will be reported to treating physicians. Patients must meet all inclusion and exclusion criteria prior to treatment. The written informed consent must be obtained from the patient prior to screening. The following criteria apply to all patients enrolled onto the study unless otherwise specified.

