3.1. Inclusion Criteria

1. Age \geq 18 years.
2. ECOG performance status of 0 or 1.
3. Adequate bone marrow function as shown by: ANC $\geq 0.5 \times 10^9/L$, Platelets $\geq 50 \times 10^9/L$, Hb ≥ 7 g/dL
4. Adequate liver function as shown by:
Total serum bilirubin ≤ 2.0 mg/dL,
ALT and AST $\leq 2.5 \times$ ULN ($\leq 5 \times$ ULN in patients with liver metastases),
Adequate renal function: serum creatinine $\leq 2.0 \times$ ULN;
5. Activating *ESR1* mutation (e.g. D538G, Y537S/N, S463P) identified on ctDNA. Novel *ESR1* alterations allowed as per discretion of PI
6. On AI with CDK4/6 inhibitor (palbociclib, ribociclib, or abemaciclib) as first line therapy for MBC for at least 12 months without evidence of clinical progression
7. Patients with histologically confirmed HR positive (ER+ and/or PR+ (>10%)), MBC

Since patients are already on AI and CDK4/6 inhibitors at the time of enrollment into the study and fulvestrant is the interventional drug, treatment can be administered as per standard of care parameters and at the discretion of treating physician

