4.2. Instructions for patients who do not start assigned protocol treatment

If a patient does not receive any assigned protocol treatment, baseline and follow-up data will still be collected. Document the reason for not starting protocol treatment on one of the baseline forms. Also report the date and type of the first non-protocol treatment that the patient receives.

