5.5. Duration of therapy

Patients will receive protocol therapy unless:

- Patient withdraws consent.
- Patient has progression of disease as defined in section 7.0.
- Patient experiences unacceptable drug toxicity.

Duration of Follow-up

For this protocol, all patients, including those who discontinue protocol therapy early, will be followed until 1 month after discontinuation of therapy for metastatic disease. Date of last follow up clinic visit should be within 30 days of end of treatment (+/- 10 days).

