7. MEASUREMENT OF EFFECT

7.1. RECIST Criteria in metastatic disease

Tumor response for patients with measurable lesions should be assessed using RECIST 1.1[32]. Patients with measurable lesions should be assessed using contrast-enhanced CT of the chest, abdomen and/or MRI scan of the chest, abdomen and pelvis approximately (+/- 7 days) every three cycles (cycle length is 28 days), from the date of first dose of fulvestrant until the 30-day follow-up visit. Although progression may be determined by the investigator based upon clinical deterioration, every effort should be made to document progression using radiographic methods. The basis for determination of progression per clinical deterioration should be documented.

Note: It is very important that the same method of radiologic assessment be used throughout the study and that the same lesions are followed.

Response Criteria

Changes in the largest diameter of the tumor lesions and the shortest diameter in the case of malignant lymph nodes should be used in RECIST assessment.

Complete Response (CR): Disappearance of all target lesions. Any pathological lymph nodes (whether target or non-target) must have reduction in short axis to <10 mm.

Partial Response (PR): At least a 30% decrease in the sum of the diameters of target lesions, taking as reference the baseline sum diameters.

Progressive Disease (PD): At least a 20% increase in the sum of the diameters of target lesions, taking as reference the smallest sum on study (this includes the baseline sum if that is the smallest on study). In addition to the relative increase of 20%, the sum must also demonstrate an absolute increase of at least 5 mm. (Note: the appearance of one or more new lesions is also considered progressions).

Stable Disease (SD): Neither sufficient shrinkage to qualify for PR nor sufficient increase to qualify for PD, taking as reference the smallest sum diameters while on study.

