9. STATISTICAL CONSIDERATIONS

Primary/Secondary Objectives:

This is a randomized, open-label, Phase II, for HR positive advanced breast cancer patients who have been treated with AI and CDK as first line in the metastatic setting for at least 12 months and who have *ESR1* mutations identified through ctDNA assay.

[name], MS, Department of Biostatistics at MD Anderson Cancer Center, will oversee the implementation of the statistical analysis. The primary endpoint is PFS, which is measured from the date of study randomization to the date of event (ie, death and/or disease progression) or the date of last follow-up if no event has occurred. Survival curves for PFS will be analyzed using the Kaplan-Meier method and survival difference across groups will be examined by log rank test. Patients alive and disease-free at the latest clinical evaluation will be censored for PFS at the date of that evaluation. We will estimate the treatment comparison with 95% confidence intervals and p-value using Cox proportional hazards regression and we will assess the proportional hazard assumption using graphs of rescaled Schoenfeld residuals and related tests. We would attempt to identify independent predictors of PFS using multivariable Cox PH regression analysis. Analysis for OS and PFS from the start of next line of therapy will be performed as described for PFS from the date of randomization. Randomization will be performed using Core. Stratification factors include recurrence free interval (\leq 3 years vs. $>$ 3 years), prior adjuvant endocrine therapy (tamoxifen vs. aromatase inhibitor), and site of metastasis (bone vs. visceral).

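### The protocol gives conflicting rules on imaging patients who stop randomised therapy before progression, so PFS could be informatively censored, with bias possible in either direction.

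*Combined protocol and SAP*

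**What the plan says.** **Setting.** Section 9 opens: "This is a randomized, open-label, Phase II, for HR positive advanced breast cancer patients". Section 3 says "The results from the screening ctDNA tests will be reported to treating physicians". Section 3.1 adds that "treatment can be administered as per standard of care parameters and at the discretion of treating physician". Section 1.6 presents the strategy as one that "precludes patients from being exposed to treatments known to be associated with resistance and unlikely to offer clinical benefit"; controls stay on the AI. Section 5.1 allows treatment under a local oncologist, with staging scans at the trial centre.

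**End of follow-up and imaging.**
- Section 5.5 follows all patients, including early stoppers, to one month after they discontinue therapy for metastatic disease. The next sentence reads: "Date of last follow up clinic visit should be within 30 days of end of treatment (+/- 10 days".
- Section 7.1 schedules scans of measurable disease "from the date of first dose of fulvestrant until the 30-day follow-up visit".
- Section 6.2 and Appendix 1 note b continue imaging until progression.

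**Analysis.** Section 9 measures PFS from randomisation to progression or death, "or the date of last follow-up if no event has occurred", and censors event-free patients at their latest clinical evaluation. It does not mention stopping early, new therapy before progression, an analysis population or a sensitivity analysis. Section 4.2, for patients who never start assigned treatment, says: "Also report the date and type of the first non-protocol treatment that the patient receives". No matching instruction covers patients who start and then stop.

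**The concern.** The log-rank test and Cox model assume that censoring carries no information about prognosis. In this trial, a control's physician knows of a mutation that the protocol itself links to AI resistance, and the alternative drug is standard of care. Some controls may therefore leave the AI before documented progression, and the decision may depend on how they are doing.

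If imaging then stops at about 30 days, their later progressions are never observed. The hazard ratio moves if leaving is related to prognosis, and the planned analyses would not show that it had moved. Scans that were not done cannot be recovered at analysis.

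**Working it through.** **1. The stated design.** Inputs from Section 9: medians 5 and 9 months, N = 124, accrual 4-5 per month, 5 months of further follow-up, two-sided alpha 5%, interim at 42 events (success if p < 0.004, futility if p > 0.72). Assumed because not stated: exponential PFS, 1:1 allocation, no dropout.

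- Design HR = 5/9 = 0.556.
- Accrual at 4.5 per month: A = 124/4.5 = 27.6 months; F = 5.
- P(event) = 1 − [exp(−λF) − exp(−λ(A+F))]/(λA), with λ = ln 2/median.
- AI: λ = 0.1386, so 1 − (0.500 − 0.011)/3.820 = 0.872.
- Fulvestrant: λ = 0.0770, so 1 − (0.680 − 0.082)/2.122 = 0.718.
- Events: 62 × (0.872 + 0.718) = 98.6.
- Fixed-design power: Φ(0.5878 × √98.6/2 − 1.96) = Φ(0.958) = 83%.
- Power with the interim rules: 81.3%, against 81% stated.

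The stated 84 events is close to the average count once early stopping is allowed for (84.8 at 5 per month, 86.4 at 4.5). The design reproduces and is a sound base for the scenarios below.

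**2. The rules side by side, for a patient who stops before progression.**

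| Source | Imaging or follow-up ends | Difficulty |
|---|---|---|
| 5.5, first sentence | 1 month after therapy for metastatic disease ends | Could mean randomised therapy or any later line |
| 5.5, second sentence | Last visit about 30 days after end of treatment | Which treatment is not said |
| 7.1 | 30-day follow-up visit | Clock starts at first fulvestrant dose, which controls do not receive |
| 6.2; Appendix 1 note b | Progression | Interval given in cycles of therapy; stopping not addressed |

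A site could follow either end point in good faith. Under 5.5 and 7.1 read as ending with randomised therapy, Section 9 censors the patient about a month after stopping.

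**3. Size.** Simulation of the design in step 1, 3,000 trials per scenario, without the interim. With nobody leaving: HR 0.55, power 82%, 98.6 events. The share of controls leaving is an assumption, shown over 10-30%. In the first three rows, leavers are followed one more month and then censored.

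| Controls who leave | 10% | 20% | 30% |
|---|---|---|---|
| Unrelated to prognosis | 0.55, 81% | 0.55, 79% | 0.55, 77% |
| 1-3 months before progression | 0.60, 67% | 0.66, 48% | 0.73, 29% |
| Those with above-median PFS | 0.53, 86% | 0.50, 91% | 0.46, 94% |
| Random, followed to progression, switch has no effect | 0.55, 83% | 0.55, 82% | 0.55, 83% |
| Random, followed to progression, switch has HR 5/9 | 0.59, 73% | 0.62, 65% | 0.65, 56% |

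The 91% and 94% are no advantage: they are rejection rates for an exaggerated effect. The third row also depends on how early those controls leave, so it shows a possible direction rather than an expected size. In a separate run of 2,000 trials per scenario, 20% of controls leaving exactly 2 months before progression gave HR 0.64 and 56% power. The same loss in both arms gave HR 0.55 and 77%.

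**The case against.** The case on the other side is substantial.

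- **Imaging until progression is already written**, in two places. Section 7.1's window starts at a fulvestrant dose, so read literally it does not govern controls at all. A reader might infer that early stoppers are scanned only to day 30; that is one of two conflicting rules, not the settled plan.
- **Section 5.5 can be read generously.** A control who changes drug is still on therapy for metastatic disease, so follow-up might continue. The secondary next-line endpoints also need later follow-up. But those endpoints start after progression, and Section 5.5's second sentence points back to the end of treatment. The ambiguity remains.
- **The protocol discourages early leaving.** Section 8 intends treatment until radiological progression, Section 5.5 lists only withdrawal, progression and toxicity as reasons to stop, and Appendix 1 note d keeps controls on their treatment. Section 7.1 accepts documented clinical deterioration as progression, so some symptomatic leavers would count as events. This lowers the likely rate but does not say how those who leave are followed or analysed.
- **Other medications are recorded** through the 30-day safety visit (Section 5.3). It would be wrong to say that switching goes unrecorded; what is missing is an instruction to record the date of, and reason for, each early stop and any later therapy.
- **The PFS definition has no on-treatment condition.** It can already be read as covering all randomised patients. This stands, and the proposed sentence makes that reading explicit.

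Two stronger readings are tempting. One is that reporting the ESR1 result to physicians is itself a defect. It is not: a positive result is the entry criterion and is known in both arms. The other is that the bias must run against fulvestrant. That needs leaving to be tied to imminent progression; random leaving causes no bias, and early departure of longer-PFS controls reverses it.

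**Conclusion.** The point holds as a conflict between stated rules that affects the primary endpoint, together with a gap in Section 9. Bias is possible, not established. It requires early stopping that differs between arms and is related to prognosis, and that sites follow the shorter rule. At an assumed 20% of controls, the hazard ratio ranges from 0.50 to 0.66 around a true value of about 0.55, and power from 91% to 48% against 82%; leaving unrelated to prognosis costs about 3 power points and no bias. The documents support neither a particular rate nor a direction. Because the direction cannot be known in advance, the rule should be fixed before data accumulate.

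**What to change.** 1. Reconcile Sections 5.5 and 7.1 with Section 6.2 and Appendix 1, so that tumour imaging in both arms is timed from randomisation and continues until progression, death or withdrawal of consent, even when randomised therapy stops early. Clarify in 5.5 which therapy is meant.
2. State in Section 9 that PFS counts the first progression or death in all randomised patients regardless of stopping or new therapy, and name this as a treatment-policy estimand.
3. Record date, reason and new therapy for every early stop, and report early stops by arm.
4. Pre-specify one sensitivity analysis that counts new anticancer therapy before progression as an event in both arms.

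**Cost.** Wording changes, a small CRF addition, one extra analysis and somewhat more follow-up; the scans are those Section 6.2 already implies. The statistical price is dilution: if 20% of controls switch and gain the assumed fulvestrant benefit, the treatment-policy result is about HR 0.62 with 65% power. Following patients removes the informative censoring but does not restore the undiluted effect, and the plan should say so.
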